Safety analyses will be conducted on the Safety population. Analyses of AEs will include 2 sets of analyses, unless otherwise specified. The first set of analyses will include data collected prior to permanent discontinuation of IP. The second set of analyses will include all data collected during the course of the entire study including the follow-up visit, regardless of IP use. Analyses of hypoglycemia will use data collected prior to permanent discontinuation of IP; while analyses for post-treatment may be performed as needed. Analyses of safety laboratory measurements will be performed on all data during the planned treatment period regardless of IP use.

Baseline is defined as the last nonmissing measurement at or before the randomization visit (Visit 8), unless otherwise specified.

CCI [REDACTED], the primary analysis method will use the copy reference approach to impute missing data based on multiple imputations with a pattern mixture model. This analysis is for the ITT estimand that will include all data collected from randomization through Week 26, regardless of IP use. The reference will be all observed data from the randomized patients in the same treatment arm who discontinue IP and complete the study without missing data. After imputation, the primary efficacy comparison will be based on the contrast between LY900014 and insulin lispro from the analysis of covariance (ANCOVA) analysis of change from baseline to Week 26 in HbA1c using all randomized patients. The model for this analysis will include the effects of treatment and strata (pooled country, type of basal insulin, and number of prandial doses at entry), and the continuous covariate of baseline value.

If there are only a limited number of patients in the reference group as described above that leads to a failure in performing the proposed multiple imputation analysis, the reference will be changed to include all observed data from all randomized patients in the same treatment arm who complete the study without missing data.

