10.3. Statistical Analyses

10.3.1. General Statistical Considerations

Statistical analysis of this study will be the responsibility of Lilly or its designee. Any change to the data analysis methods described in the protocol will require an amendment ONLY if it changes a principal feature of the protocol. Any other change to the data analysis methods described in the protocol, and the justification for making the change, will be described in the statistical analysis plan (SAP) or the clinical study report (CSR). Additional exploratory analyses of data will be conducted, as deemed appropriate.

The primary analysis is for the treatment period through Week 26.

Efficacy analyses will be conducted on all randomized patients according to the treatment the patients are assigned. The analyses for the primary and multiplicity adjusted objectives will be performed for the efficacy estimand including data collected prior to permanent discontinuation of IP and for the ITT estimand including all data collected regardless of IP use (Section 10.3.3.1). Unless otherwise specified, the efficacy analyses for other secondary objectives and exploratory objectives will be performed for the efficacy estimand. When change from baseline is included as a response variable of analysis models, the patient will be included in the analysis only if a baseline and at least 1 postbaseline measurement are available. Selected efficacy analyses will also be conducted using the Per Protocol (PP) and Completer populations.

Safety analyses will be conducted on the Safety population. Analyses of AEs will include 2 sets of analyses, unless otherwise specified. The first set of analyses will include data collected prior to permanent discontinuation of IP. The second set of analyses will include all data collected during the course of the entire study including the follow-up visit, regardless of IP use. Analyses of hypoglycemia will use data collected prior to permanent discontinuation of IP; while analyses for post-treatment may be performed as needed. Analyses of safety laboratory measurements will be performed on all data during the planned treatment period regardless of IP use.

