10.3.3. Efficacy Analyses

10.3.3.1. Primary Analyses

The primary objective of this study is to test the hypothesis that LY900014 is noninferior to insulin lispro on glycemic control (NIM=0.4% for HbA1c) in patients with T2D, when administered as prandial insulin (0-2 minutes prior to the meal), in combination with basal insulin for 26 weeks. There will be 2 primary analysis methods, each tested at the full significance level of 0.05.

CCI, the primary analysis method will use the copy reference approach to impute missing data based on multiple imputations with a pattern mixture model. This analysis is for the ITT estimand (treatment regimen estimand) that will include all data collected from randomization through Week 26, regardless of IP use. The reference will be all observed data from the randomized patients in the same treatment group who discontinue IP and complete the study without missing data. After imputation, the primary efficacy comparison will be based on the contrast between LY900014 and insulin lispro from the ANCOVA analysis of change from baseline to Week 26 in HbA1c using all randomized patients as described in Section 10.3.1.

If there are only a limited number of patients in the reference group as described above that leads to a failure in performing the proposed multiple imputation analysis, the reference will be changed to include all observed data from all randomized patients in the same treatment arm who complete the study without missing data.

CCI, the primary efficacy comparison will be based on the contrast between LY900014 and insulin lispro at Week 26 (Visit 18) from the MMRM analysis of change from baseline in HbA1c including data collected from all randomized patients prior to permanent discontinuation of IP through Week 26 (efficacy estimand). The analysis model and selection of covariance structure is described in Section 10.3.1.

For both primary analysis approaches, LY900014 will be declared noninferior to insulin lispro if the upper limit of the 2-sided 95% CI for the LS mean difference in the change from baseline in HbA1c for LY900014 minus insulin lispro is below +0.4%. In addition, the 95% CI for the treatment difference will be compared to an alternative NIM of +0.3%. Both estimands will be tested at the full significance level of 0.05.

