6.1. General Considerations

Statistical analysis of this study will be the responsibility of Eli Lilly and Company (hereafter Lilly). Any change to the data analysis methods described in the protocol will require an amendment ONLY if it changes a principal feature of the protocol. Any other change to the data analysis methods described in the protocol, and the justification for making the change, will be described in this SAP and/or in the clinical study report (CSR). Additional exploratory analyses will be conducted, as deemed appropriate.

Statistical analyses for Japan are described in [Appendix 2](#). Statistical Analyses for the Maximum Extended Enrollment (MEE) Addendum are described in [Appendix 3](#).

For purposes of analysis, the following populations are defined in [Table 6.1](#):

Table 6.1. Patient Populations

Population	Description
Entered	All patients who give informed consent.
Enrolled	All patients who receive at least 1 dose of open-label insulin lispro in the 8-week lead-in period.
Randomized	All patients who are randomly assigned to study treatment at Visit 8. Treatment group will be defined on the basis of the treatment the patients are assigned.
Safety	All randomized patients who receive at least 1 dose of the randomly assigned investigational product (IP). Treatment group will be defined on the basis of the treatment the patients are assigned.
Completer	Patients included in the randomized population who have completed Week 26 of study treatment without permanent discontinuation of IP. Treatment group will be defined on the basis of the treatment the patients are assigned.
Per Protocol	Patients included in the randomized population who have completed Week 26 of study treatment without permanent discontinuation of IP and without significant protocol deviations through Week 26 that would significantly impact the primary objective. Treatment group will be defined on the basis of the treatment the patients actually receive.

Unless otherwise stated, the efficacy analyses will be conducted on the Randomized Population, and the safety analyses will be conducted on the Safety Population.

The primary analysis is for the treatment period through Week 26.

Unless otherwise noted, all tests of treatment effects will be conducted at a 2-sided alpha level of 0.05, and CIs will be calculated at 95%, 2-sided. All tests of interactions between treatment groups and other factors will be conducted at a 2-sided alpha level of 0.10.

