Table 6.2. Baseline and Post-Baseline Definitions and Patient Population by Study Period and Type of Analysis

Study Period/Analysis	Patient Population	Baseline Observations	Post-Baseline Observations
Lead-In Period			
TEAEs	All Enrolled Patients	Prior to first dose of open-label insulin lispro (or Visit 2 date if the dose date is missing)	The entire lead-in period after first dose of open-label insulin lispro and prior to the first dose of IP (or Visit 8 date if the dose date is missing).
Basal, prandial, and total insulin doses, and prandial/total insulin dose ratios continuous analysis	All Randomized Patients	Visit 2	Visits 3 to 8 prior to initiation of IP
Weight MMRM and ANCOVA	All Randomized Patients	Last of Visits 1-2	Visits 3–8 AND Last of Visits 3-8
26-Week Treatment Period (including Safety Follow-Up Visit where applicable)			
HbA1c MMRM and ANCOVA (efficacy estimand)	All Randomized Patients with a baseline and at least 1 post-baseline observation while on IP	Last of Visits 7-8	Visits 11, 13, 15, and 18 prior to discontinuation of IP AND Last of Visits 9-18 prior to discontinuation of IP
HbA1c ANCOVA (ITT estimand)	All Randomized Patients with a baseline and at least 1 post-baseline observation	Last of Visits 7-8	Visit 18 with imputation for patients who discontinue study prior to Visit 18
HbA1c categorical analyses longitudinal logistic regression and LOCF logistic regression	All Randomized Patients with a baseline and at least one post-baseline observation while on IP	Last of Visits 7-8	Visits 11, 13, 15, and 18 prior to discontinuation of IP AND Last of Visits 9-18 prior to discontinuation of IP
1-hr and 2-hr PPG and other MMTT variables (efficacy estimand)	All Randomized Patients with a post-baseline observation while on IP	Visit 8 prior to initiation of IP	Visit 18 prior to discontinuation of IP
1-hr and 2-hr PPG and other MMTT variables (ITT estimand)	All Randomized Patients with a post-baseline observation	Visit 8 prior to initiation of IP	Visit 18 regardless of IP use
10-point SMBG, basal, prandial insulin doses, prandial/total insulin dose ratios	All Randomized Patients with a baseline and at least one post-baseline observation	Visit 8 prior to initiation of IP	Visits 11, 13, 15, and 18 prior to discontinuation of IP AND Last of Visits 9-18 prior to discontinuation of IP

Baseline and Post-Baseline Definitions and Patient Population by Study Period and Type of Analysis

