6.11. Efficacy Analyses

6.11.1. Primary Outcome and Methodology

The primary objective of this study (H1) is to test the hypothesis that LY900014 is noninferior to insulin lispro on glycemic control (NIM=0.4% for HbA1c) in patients with T2D, when administered as prandial insulin (0 to 2 minutes prior to the meal), in combination with basal insulin for 26 weeks. There will be 2 primary analysis methods, each tested at the full significance level of 0.05.

CCI [REDACTED], the primary analysis method will use the copy reference approach to impute missing data based on multiple imputations with a pattern mixture model. This analysis is for the ITT estimand that will include all data collected from randomization through Week 26, regardless of IP use. The reference will be all observed data from the randomized patients in the same treatment group who discontinue IP and complete the study without missing data. After imputation, the primary efficacy comparison will be based on the contrast between LY900014 and insulin lispro from an ANCOVA. The model for the change from baseline to the Week 26 HbA1c endpoint will include treatment and strata (pooled country, type of basal insulin, and number of prandial doses at study entry) as fixed effects and baseline HbA1c as a covariate.

If there are only a limited number of patients in the reference group as described above that leads to a failure in performing the proposed multiple imputation analysis such that the model cannot converge, or the number of records without missing data is less than the number of records with missing data, the missing HbA1c measurement at Week 26 will be imputed by the patient-level observed baseline value plus a noise, assuming a washout of any potential treatment effect (or “return to baseline”). The noise follows a normal distribution with the variability estimated from the “washout HbA1c data.” The “washout HbA1c data” will be derived by subtracting the corresponding treatment mean at Week 26 from individual non-missing HbA1c values at Week 26.

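### The protocol gives two different populations for the primary ITT HbA1c analysis, and SAP Table 6.2 adopts the narrower one, so randomized patients with no post-baseline HbA1c are left out instead of imputed

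*SAP*

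**What the plan says.** **Protocol, all randomized patients.** Section 10.3.3.1 describes the analysis after multiple imputation as the "ANCOVA analysis of change from baseline to Week 26 in HbA1c using all randomized patients as described in Section 10.3.1". The synopsis gives the same population: "change from baseline to Week 26 in HbA1c using all randomized patients".

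**Protocol, restricted set.** Section 10.3.1 says that, where change from baseline is the response, "the patient will be included in the analysis only if a baseline and at least 1 postbaseline measurement are available". The synopsis repeats this sentence. In both places it comes soon after the two estimands are named, and neither place exempts the ITT analysis.

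**SAP.** Section 6.1 sets a default: "Unless otherwise stated, the efficacy analyses will be conducted on the Randomized Population". Table 6.2 then states otherwise for the row HbA1c ANCOVA (ITT estimand), where the population is "All Randomized Patients with a baseline and at least 1 post-baseline observation". The last column of that row reads "Visit 18 with imputation for patients who discontinue study prior to Visit 18".

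**Imputation.** SAP 6.11.1 plans copy reference first, drawing on same-arm patients who stopped IP and completed the study. If that fails, "the missing HbA1c measurement at Week 26 will be imputed by the patient-level observed baseline value plus a noise".

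This analysis is one of two primary analyses, each at the full 0.05 level (SAP 6.11.1). It also serves the HbA1c superiority test, H4 (SAP 6.11.2).

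**The concern.** Requiring one post-baseline value is natural for an MMRM or an LOCF analysis, which cannot use a patient without one. An analysis that imputes Week 26 does not need it. Applied here, the rule excludes patients by what they did after randomization, in the analysis meant to follow patients as assigned.

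The Table 6.2 row also works against itself. A patient who leaves the study with no HbA1c sample has discontinued before Visit 18, so the last column calls for imputation while the population column removes the patient.

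At stake is whether the estimate matches the stated estimand. The earliest leavers would not contribute to H1 or H4 under the ITT estimand. If the delta analysis in SAP 6.11.4 uses the same set, they would not be stress-tested either. That section does not state its population.

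**Working it through.** **1. The plan's power figure.** Inputs (Protocol 10.1): margin 0.4, SD 1.1, true difference 0, 284 completers per group, two-sided 95% CI.

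- SE = 1.1 × √(2/284) = 0.0923
- Power = Φ(0.4/0.0923 − 1.96) = Φ(2.37) = 0.991, which reproduces the stated figure of more than 99%.
- All 670 analysed (335 per group): SE = 1.1 × √(2/335) = 0.085 and power = 0.997.
- Dropping 1% to 5% of the 670 (7 to 34 patients, an assumed range): power 0.997 to 0.996.
- Dropping all 102 planned non-completers returns to 284 per group and 0.991.

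Power is therefore not the issue.

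**2. How many patients could be affected.** Planned non-completers: 670 − 568 = 102 (15.2%). The first scheduled post-baseline HbA1c is Visit 11, Week 4 (Schedule of Activities; SAP Table 6.2). Assume uniform dropout over 26 weeks, that all 102 leave the study, and that none gives a sample on leaving:

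- 102 × 4/26 = 15.7, about 16 patients (2.3% of 670).

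Two of these assumptions push the figure up:

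- Protocol 5.3.1 asks patients who leave the study to attend an early-discontinuation visit. The Schedule of Activities appears to include HbA1c there (its columns are partly broken in the text available), and footnote b waives laboratory tests only for lead-in discontinuers.
- The synopsis and Section 5.2 describe the 568 as completing 26 weeks of treatment, whereas Section 10.1 says completing the study. Patients who stop IP may stay, with HbA1c collected (Section 8.1).

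Front-loaded dropout would push the other way. About 16 is an upper-range illustration, not an estimate.

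**3. Effect on the treatment difference.** Let m be the mean HbA1c change among patients kept, equal in both arms, and let the dropped patients be restored at zero change (return to baseline). With a dropped on LY900014, b on lispro and 335 per arm:

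- Shift in (LY900014 − lispro) = |m| × (a − b)/335

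| Dropped (LY900014 vs lispro) | Assumed reduction in points | Shift | Shift / 0.085 |
|---|---|---|---|
| Equal numbers | any | 0 | 0 |
| 17 vs 3 | 0.3 | 0.3 × 14/335 = 0.013 | 0.15 |
| 17 vs 3 | 0.4 | 0.4 × 14/335 = 0.017 | 0.20 |
| 17 vs 3 | 0.6 | 0.6 × 14/335 = 0.025 | 0.29 |

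The 17 versus 3 split is a deliberate worst case. It totals 20, more than the 16 above, and nothing in the documents suggests such an imbalance. The mean reductions are also assumed.

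**4. Against the decision rules.** A shift of 0.013 to 0.025 is 3% to 6% of the 0.4 margin. Superiority has no margin to absorb it. Against a plain 1.96 cutoff, a 0.20 SE shift would raise one-sided error from 2.5% to 1 − Φ(1.76) = 3.9%, in that extreme case only. The level actually available to H4 depends on the graphical scheme.

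**The case against.** A reader might infer that the SAP departs from the protocol. The documents do not support that. The restriction is already in the protocol synopsis and Section 10.3.1, and the sentence in Section 10.3.3.1 that promises all randomized patients refers to Section 10.3.1. The SAP applies one of two conflicting protocol statements. This stands, and it places the fault inside the protocol. It does not settle which statement should govern an imputed analysis.

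A second objection is that few or no patients may be affected. Anyone who attends an early-discontinuation visit may have a post-baseline HbA1c. This also largely stands, with one gap: Table 6.2 does not say whether such a value satisfies the rule for this row.

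Third, no harm to a conclusion is shown. For H1 that is right. A reader might also suppose that early leavers go because of tolerability or hypoglycemia on LY900014, but the documents give no evidence of this, so no direction of bias can be asserted.

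Finally, SAP 6.3 on missing data is largely redacted and could bear on the point. That limits certainty about how these patients are handled, but it does not remove the contradiction in the visible text.

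**Conclusion.** The concern holds as an inconsistency in the primary ITT population that Table 6.2 resolves in the restrictive direction. Followed as written, the table excludes randomized patients with no post-baseline HbA1c from H1 and H4 under the ITT estimand. The fallback imputation does not need that exclusion, and the row's own imputation instruction points the other way.

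The likely effect is small: probably fewer than about 16 patients, close to no bias if losses are balanced, and 0.013 to 0.025 points in an extreme unbalanced case. These sizes rest on uniform dropout, equal mean change among the patients kept, return to baseline for those dropped, and an assumed mean reduction of 0.3 to 0.6 points. The stronger inference that noninferiority or power is in doubt is not supported, since power stays at 0.991 or above throughout. The change is worth making before unblinding because it aligns the analysis with its stated estimand at almost no cost.

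**What to change.** 1. In SAP Table 6.2, row HbA1c ANCOVA (ITT estimand), set the population to all randomized patients with a baseline HbA1c. Impute Week 26 for every patient who lacks it, including those with no post-baseline value.
2. State that the same set is used for H4 under the ITT estimand and for the ITT delta analysis in SAP 6.11.4.
3. Exempt the multiply imputed ITT analysis from the one-post-baseline rule in both Protocol Section 10.3.1 and the synopsis. Alternatively, record the exemption and its reason in the SAP, as SAP 6.1 allows for changes that do not alter a principal feature of the protocol.

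The cost is one table cell, a clarifying sentence in the SAP, and either two short protocol edits or a recorded justification. No new data are needed and the sample size does not change. If early losses are heavier on LY900014, the estimate becomes slightly less favourable to it.

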The definitions of baseline and post-baseline for the efficacy and safety analyses depend on which analysis period is being used. The following analysis periods will be used:

- Lead-in Period – Visits 2 to 8
- 26-Week Treatment Period – from randomization to Week 26 prior to discontinuation of IP and from randomization to Week 26 (including all data regardless of IP use)
- 26-Week Treatment Period and Safety Follow-Up Visit – from randomization to Visit 801 (including all data regardless of IP use)

The data on IP is defined based on the following rules:

- For data only measured at an office visit
 - MMTT postbaseline data will be classified as on IP if the MMTT performance date is prior to or on the last IP dose date
 - Other postbaseline data (for example, vital signs, safety laboratory tests, and questionnaires) will be considered as on IP if the measurement was performed at or prior to the cutoff date defined as 14 days after the last IP dose date
- For data collected as running records with an exact date stamp such as adverse events (AEs) and diary entries where the dates of the measures were not tied with the date of an office visit, postbaseline data with dates \leq (last study drug dose date +1) will be considered as data on IP.

Table 6.2 describes the rules for determining the patient population, baseline and postbaseline observations for the different analysis periods.

For continuous measures, summary statistics will include sample size, mean, SD, median, minimum, and maximum for both the actual and the change from baseline measurements. Least-squares (LS) means and standard errors derived from the analysis models will also be displayed. Treatment comparisons will be displayed showing the treatment difference LS means and the 95% CIs for the treatment differences, along with the p-values for the treatment comparisons.

For categorical measures, summary statistics will include sample size, frequency, and percentages. Fisher's exact test or Pearson's chi-square test will be used for treatment comparisons.

For laboratory values, both conventional (CN) and Systeme International (SI) units will be presented. Therefore, both % and mmol/mol will be presented for HbA1c and both mg/dL and mmol/L will be presented for glucose measurements.

All baseline measures will be analyzed using an analysis of variance (ANOVA) model that has treatment as the model term.

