6.11.2. Analyses of Multiplicity Adjusted Objectives

A graphical approach for multiple comparisons (Bretz et al. 2011) will be used to strongly control the overall Type I error (2-sided alpha level of 0.05) for testing the treatment effect for the primary and the following multiplicity adjusted objectives: superiority of LY900014 compared with insulin lispro for (H2) 1-hour postprandial plasma glucose (PPG) excursion at the study primary endpoint, (H3) 2-hour PPG excursion at the study primary endpoint, and (H4) change from baseline to the study primary endpoint in HbA1c. Analyses will be performed for both the efficacy estimand and ITT estimand.

The graphical testing scheme for this study is displayed in [Figure 6.1](#). All the hypotheses are connected by lines with arrowheads indicating the directions of testing paths. The initial allocation of study total alpha for each hypothesis is located within the same node of the hypothesis. In this study, the study total alpha level (0.05) will be all used for the primary objective (H1) in the initial step. Then, the study total alpha level (0.05) will be allocated to other objectives according to the values of transition weights shown above the connecting lines in the figure once H1 is met. If 1 of the remaining objectives is successfully demonstrated with the given alpha level, its alpha will be allocated to the rest of objectives by the transition weights in the paths. The iterative test procedure continues until none of the remaining objectives can be demonstrated with their preserved alphas or all objectives are demonstrated successful.

An ANCOVA model with strata (pooled country, type of basal insulin, number of prandial doses at study entry, and HbA1c stratum) and treatment as fixed effects and baseline as a covariate will be used to analyze the 1-hour and 2-hour PPG excursions for both the efficacy (data collected prior to discontinuation of IP) and ITT (all data collected regardless of IP use) estimands. However, if the percentage of the patients with missing MMTT data at baseline is higher than 15%, a constrained longitudinal data analysis model (Liu et al. 2009; Lu 2010) will be used instead.

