6.11.4. Sensitivity Analyses for Missing Data

A missing-not-at-random (MNAR)-based analysis will be performed for both the efficacy and ITT estimands to assess sensitivity to departures from the missing-at-random (MAR) assumption by repeatedly adjusting the imputations of missing data to provide a progressively more severe stress test (Ratitch et al. 2013). The basic idea is to impute the missing values and add a value (delta) to the imputed values of the experimental treatment group and perform an analysis for the primary endpoint on the delta-adjusted data set to see whether the conclusion of the primary analysis is overturned. If not, a larger delta is chosen and the process repeated until the primary result is overturned. If the delta required to overturn the primary result is not a plausible departure from MAR, then the primary result is robust to plausible departures from MAR. Imputation under the noninferiority null method (where delta equals the NIM) will be included as a special case of the progressive stress test.

For the ITT estimand, the reference group will be as described for the **CC1** primary analysis, and ANCOVA on the change from baseline to Week 26 in HbA1c will be used.

For the efficacy estimand, the reference group will be the insulin lispro treatment group. Imputation will be for all longitudinal visits.

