6.11.5. Other Secondary Efficacy Analyses

The analyses described in Section 6.11.5 to Section 6.11.7 will include data collected from all randomized patients prior to permanent discontinuation of IP. The longitudinal observations of actual and change from baseline in HbA1c up to Week 26 will be analyzed using the same MMRM model as for the analysis of the primary outcome. For the following secondary efficacy endpoints, an MMRM model similar to that for the primary outcome with an additional term of HbA1c stratum ($\leq 8\%$, $> 8\%$) will be used:

- actual and change from baseline 1,5-AG values
- actual and change from baseline 10-point SMBG values (fasting, 1 hour post morning meal, 2 hours post morning meal, pre midday meal, 1 hour post midday meal, 2 hours post midday meal, pre evening meal, 1 hour post evening meal, 2 hours post evening meal, and bedtime)
- actual and change from baseline in total, basal, and prandial insulin doses and prandial/total insulin dose ratios

Three 10-point SMBG profiles are expected to be collected during the 2 weeks prior to specified visits. Valid SMBG profiles will be used for analysis, defined as having non-missing values at ≥ 6 time points among the 10 pre-specified time points and being collected during 2 weeks prior to a given visit. For each time point, the average of the corresponding SMBG values from the valid SMBG profiles will be used for analysis. The excursion of SMBG for each meal category (that is, morning meal, midday meal, and evening meal) calculated using the average values at the corresponding time points will be used for analysis.

The following endpoints, collected from the MMTT, will be analyzed using the ANCOVA model with strata (pooled country, type of basal insulin, number of prandial doses at study entry, and HbA1c stratum) and treatment as fixed effects and baseline as a covariate:

- actual and change from baseline in fasting glucose (average of measurements at time -15 and 0), and PPG at 15, 30, 60, 120, 180, and 240 minutes after the meal
- PPG excursions at time 15, 30, 180, and 240 minutes after the meal (PPG minus fasting glucose)

Sensitivity analysis for PPG excursions may be performed to exclude patients whose PPG excursion could be affected by factors including MMTT consumption amount (for example, partial MMTT was consumed) and correction bolus insulin usage.

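### As visibly written, the ITT-estimand tests of 1-hour and 2-hour PPG excursion (H2, H3) use only patients with a Visit 18 MMTT, while the ITT-estimand HbA1c tests (H1, H4) impute missing Week 26 values

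*SAP*

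**What the plan says.** SAP Table 6.2 has a separate row for each endpoint and estimand. For 1-hour and 2-hour PPG under the ITT estimand, the population is "All Randomized Patients with a post-baseline observation" and the data are "Visit 18 regardless of IP use". For HbA1c under the ITT estimand, the data are "Visit 18 with imputation for patients who discontinue study prior to Visit 18".

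SAP 6.11.2 applies one ANCOVA to the excursions for both estimands and changes only the data cut, the second being "and ITT (all data collected regardless of IP use) estimands". SAP 6.11.1 gives the HbA1c ITT rule. It is copy-reference multiple imputation from patients in the same arm who stopped IP but completed the study. A return-to-baseline fallback applies if that group is too small. SAP 6.11.2 tests H4 by the same analysis as H1, so H4 is imputed too.

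Protocol 9.1.4.4 schedules the MMTT at Visits 8 and 18 only. SAP 6.1 separates the two PPG data cuts: "MMTT postbaseline data will be classified as on IP if the MMTT performance date is prior to or on the last IP dose date". Protocol 10.3.3.2 says that the multiplicity-adjusted objectives are analysed for both estimands as in Protocol 10.3.3.1, where the ITT imputation is described. SAP 6.3, on dropouts and missing data, is redacted after its first paragraph.

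**The concern.** H2 and H3 are superiority hypotheses inside the alpha-controlled sequence, and each is to be reported under an estimand that the protocol calls the treatment-regimen estimand. An observed-case test answers that question only if patients without a Visit 18 MMTT would have shown the same treatment difference as those with one, given arm, baseline and strata.

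For patients who leave, that is a weak assumption. Under Protocol 7.8.2, patients who stop IP go back to their prestudy prandial insulin or to another rapid-acting analogue. Under 7.8.1, LY900014 is not supplied after the study. A meal excursion reflects the insulin injected at that meal, so there is little reason to expect a leaver to keep the LY900014 effect. The sponsor already assumes washout for HbA1c in the SAP 6.11.1 fallback. If leavers lose the benefit, leaving them out favours LY900014, and no visible PPG analysis would show by how much.

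**Working it through.** **1. The plan's own figures.** Inputs from Protocol 10.1 and SAP 5.2 are a margin of 0.4%, true difference 0, SD 1.1% and 284 completers per arm. Power = Φ(0.4 / (1.1 × √(2/284)) − 1.96) = Φ(0.4/0.0923 − 1.96) = 99.1%, which agrees with the stated figure of at least 99%. Planned non-completers are 670 − 568 = 102, and 102/670 = 15.2%. This fits a 15% allowance: 568/0.85 = 668.2, rounded up to 669, against about 670 stated.

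**2. Does any visible provision cover a missing Visit 18 MMTT?**

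| Provision | Why it does not apply |
|---|---|
| LOCF default for ANCOVA (Protocol 10.3.1) | It carries post-baseline values only, and there is no earlier post-baseline MMTT |
| Constrained longitudinal model (SAP 6.11.2) | Triggered "if the percentage of the patients with missing MMTT data at baseline is higher than 15" percent, so by missing baseline data |
| Delta adjustment (SAP 6.11.4) | The instruction is to "perform an analysis for the primary endpoint on the delta-adjusted data set", which is HbA1c |
| PPG sensitivity analysis (SAP 6.11.5) | "Sensitivity analysis for PPG excursions may be performed to exclude patients whose PPG excursion could be affected by factors including MMTT consumption amount"; it removes more patients |
| Return-to-baseline fallback (SAP 6.11.1) | Written for the Week 26 HbA1c value |

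**3. Size of the possible overstatement.** Let d be the effect in patients with the test, m the share without it (equal in both arms), and f the share of d that the omitted patients keep. The all-randomised effect is (1 − m)d + m·f·d = d[1 − m(1 − f)]. The observed-case effect is d, so the ratio of observed-case to all-randomised is 1/[1 − m(1 − f)].

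| Missing m (patients of 670) | f = 1 | f = 0.5 | f = 0 |
|---|---|---|---|
| 5% (34) | 1.000 | 1.026 | 1.053 |
| 10% (67) | 1.000 | 1.053 | 1.111 |
| 15.2% (102) | 1.000 | 1.082 | 1.180 |

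For example, with m = 0.152 and f = 0, the ratio is 1/0.848 = 1.180. The values of m and f are assumptions; only 15.2% comes from the plan.

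**4. What imputation would do.** If imputed patients carry no treatment difference, the estimate becomes (1 − m) of the observed-case value: 0.95, 0.90 and 0.848. That is correct if f = 0. If f = 1, it understates the effect by 5%, 10% and 15%. A simulation applied baseline-plus-noise to every missing excursion. It assumed 670 patients, an effect of 0.25 SD, baseline correlation 0.3 or 0.5, random missingness, 10 imputations and 500 trials per setting. The test statistic fell to about 0.93, 0.86–0.88 and 0.80–0.83 of the observed-case value at the three levels.

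**The case against.** The strongest reply is that the rule may lie in the redacted part of SAP 6.3, whose visible opening covers the primary and multiplicity-adjusted objectives. This stands to the extent that a reader may not infer that the plan has no rule for missing PPG data. It does not settle the point. A hidden imputation rule would conflict with the visible population column of Table 6.2. A hidden observed-case rule would agree with the table, but would leave a complete-case test under a treatment-regimen label. The pointer in Protocol 10.3.3.2 can be read as carrying imputation over to PPG or only as naming the two data cuts.

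Second, the visible SAP defines the ITT estimand by which data count, not by an imputation method, and observed-case ANCOVA is unbiased if missingness depends only on arm, baseline and strata. Both statements are correct. The difficulty is that this assumption is least plausible for patients no longer on LY900014, and no visible PPG analysis tests it.

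Third, return-to-baseline for everyone would replace one untestable assumption with another. It would treat patients still on IP who merely missed the test as washed out. With dropout that depends on arm and baseline (assumed log-odds 0.4 for arm and 0.6 per baseline SD), it understated a fully kept effect by 22–24% at 15.2% missing. This objection stands, and the fix below therefore separates patients off IP from those still on it.

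A reader might also infer that the two estimands' PPG tests are nearly the same analysis, because Protocol 9.1.4.4 describes the Visit 18 MMTT only with blinded study insulin. The documents do not support that. Protocol 5.3.1 has patients who stop IP but stay in the study complete the remaining visits, and the third SAP version added an on-IP definition specifically for the MMTT. How many off-IP tests there will be is unknown.

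**Conclusion.** The point holds on the visible text. H2 and H3 under the ITT estimand are tested only in patients with a Visit 18 MMTT, while H1 and H4 under the same name are imputed. The possible overstatement of the ITT excursion effect is at most about 18%, reached only if all 102 planned non-completers lack the test and keep none of the effect. It is 5% to 11% at 5% to 10% missing with no effect kept, and nil if omitted patients keep the full effect.

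The 18% is an upper illustration, not an expected bias. Protocol 5.2 counts the 568 as completing treatment and Protocol 10.1 as completing the study. Some patients who stop IP may still attend Visit 18. In the other direction, a completer can also miss the test, because Protocol 9.1.4.4 requires fasting glucose in range and allows only two reschedulings. Such a patient, if still on IP, would be expected to keep the effect.

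A reader might infer inflated Type I error or lost power. Neither is claimed: the working concerns the size of the estimate, and the visible text gives no PPG effect size, SD or power, so a power figure would have no basis in the plan.

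**What to change.** In SAP Table 6.2 and SAP 6.11.2, analyse H2 and H3 under the ITT estimand in all randomised patients, with two rules for a missing Visit 18 excursion:

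- **Off IP:** multiply impute under the washout logic of SAP 6.11.1. Use off-IP patients in the same arm with a Visit 18 MMTT as reference if there are enough, otherwise baseline excursion plus noise.
- **Still on IP:** multiply impute under missing at random within arm.

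Keep the constrained longitudinal option for missing baseline MMTT data, and do not add a requirement for a baseline MMTT. Report the observed-case ANCOVA alongside as a sensitivity analysis. If the sponsor prefers observed cases as the main analysis, label it so and prespecify the imputation above as the sensitivity analysis for H2 and H3. If the redacted part of SAP 6.3 already imputes MMTT data, correct the Table 6.2 row to match and refer to that rule.

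The cost is SAP wording and some programming, with no new data. The ITT PPG result may be smaller and less precise. The simulated losses above apply baseline-plus-noise to every missing value, so the loss should be smaller when it is confined to patients off IP.
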